2.2.1.2 Secondary safety variables

The secondary safety variable is the withdrawal from the study due to TEAEs. This is measured by the incidence of TEAEs leading to study discontinuation and/or permanent withdrawal of study medication.

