- Action taken with IMP: dose not changed, dose reduced, dose increased, drug temporarily, interrupted, drug permanently withdrawn or not applicable
- Outcome: resolving, not resolved, resolved, resolved with sequelae, worsened, fatal or unknown

AEs (including SAEs) are characterized as either non-treatment-emergent or treatment emergent according to the following criteria:

- Non-treatment emergent AEs are those with onset date after a 140-day period after the end date of study medication.
 - Any AE occurring more than 140 days after the last administration of study medication in AS0008 and prior to the first administration of study medication in AS0009 will also be considered as non-treatment emergent, and will therefore be excluded from the summary tables. Such events will be included in the listings.
- TEAEs are those with onset date on or after the start date of study medication in AS0009.
- Events that were ongoing at the end of AS0008 will have their treatment-emergent status taken from the AS0008 database.

For all AEs the following variables will be calculated (see [Section 10.2.1](#)):

- Duration.
- Time since first bimekizumab dose.
- Time since last/latest bimekizumab dose.

AE summaries will, in general, include only events with onset on or after the start date of study treatment in AS0009. Certain displays will be repeated including all AEs in AS0008 (with the exception of those with onset during placebo treatment) and AS0009 as outlined below. These displays will include only subjects from AS0008 who were enrolled in AS0009.

In general, the attributes of these events (for AEs that started and were resolved in AS0008) will be taken from the AS0008 database. However, the identification of Safety Topics of Interest will be made across all events in AS0008 and AS0009 using the criteria defined in this SAP.

For events which were ongoing at the end of AS0008, the following rules will be implemented:

- Onset date (and derived variables) will be taken from the AS0008 database
- End date, outcome, actions taken and seriousness will be taken from the AS0009 database.
- In order to ensure that AEs are not duplicated in the outputs these will be merged across the studies by Subject ID, verbatim term (AETERM), dictionary-derived term (AEDECOD), start date (AESTDTC), relationship (AEREL) and severity (AESEV) to create one record for the specific event.

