Summaries of AEs in AS0008 and AS0009 will include AEs with onset on the first dose of bimekizumab in AS0008 up to 140 days after the last dose of bimekizumab in AS0009. AEs which occur on the day of a treatment switch will be considered to have begun on the previous treatment, with the exception of the following AEs which will be considered to have begun on the new treatment:

- Events that fulfill the anaphylaxis criteria for acute events (see [Section 10.2.3](#)).
- Events that fulfill the hypersensitivity reaction criteria for (see [Section 10.2.3](#)).
- Events with a HLT of “Administration site reactions NEC”.
- Events with an HLT of “Injection site reactions”.

AEs which occur on the first day of bimekizumab treatment in AS0008 following initial treatment with placebo will not be included in the summaries, unless they fulfill 1 of the 4 exception criteria above. AEs which occur after the last dose of bimekizumab in AS0009 and up to 140 days after the last dose of bimekizumab in AS0009 will be assigned to bimekizumab 160mg.

AEs will be presented as “number of subjects (percentage of subjects) [number of events]”. “[number of events]” will include all cases of an AE including repeat occurrences in individual subjects, while “number of subjects” will count each subject only once.

An overview of TEAE (number and percentage of subjects with any TEAE, serious TEAE, TEAE leading to study discontinuation, TEAE leading to permanent withdrawal of study medication, drug-related TEAE, severe TEAE, fatal AE [see note below], fatal TEAE and TEAE with missing seriousness) will be provided by treatment group at completion of AS0008 and overall. This summary will be repeated by SS Sub-population. It will also be repeated including all TEAEs in AS0008 and AS0009 reported for subjects in the AS0009 SS (with the exception of those with onset during placebo treatment) combined.

The category for fatal AEs will be based on all subjects enrolled in AS0009 in all the above summaries.

The following categories of TEAE will be summarized by MedDRA SOC, HLT and PT, including EAIR and EAER (calculated as described in [Section 10.2.2](#)), where all summaries refer to AEs reported in AS0009 only except where stated:

- All TEAEs by treatment group at completion of AS0008 and overall.
- All TEAEs by treatment group at completion of AS0008 and overall, by SS Sub-population.
- Serious TEAEs by treatment group at completion of AS0008 and overall.

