- Serious TEAEs by treatment group at completion of AS0008 and overall, by SS Sub-population.
- All TEAEs in AS0008 and AS0009 by treatment at time of AE onset (BKZ 160mg, BKZ 320mg and BKZ Total).
- Serious TEAEs in AS0008 and AS0009 by treatment at time of AE onset (BKZ 160mg, BKZ 320mg and BKZ Total).

- All TEAEs AS0008 and AS0009 by timing of onset relative to ADAb status in AS0008 and AS0009. This will include columns for the following:
 - TEAEs starting before the first ADAb positive result in AS0008 and AS0009 (includes ADAb Categories 2b only)
 - TEAEs starting on the same date or after the first ADAb positive result in AS0008 and AS0009 (includes ADAb Categories 2b, 3b, 4b, 5b and 6b)
 - TEAEs for subjects who are ADAb negative at all time points in AS0008 and AS0009 (includes ADAb Categories 1b only)

Note that any TEAEs occurring for a subject who was ADAb positive at AS0008 Baseline will therefore all occur after ADAb positivity; such subjects will be excluded from the first column in the above table. Subjects in Category 9b (missing) will not be included in the table.

The following categories of TEAE will be summarized by MedDRA SOC, HLT and PT, by treatment group at completion of AS0008 and overall:

- TEAEs leading to study discontinuation and/or permanent withdrawal of study medication.
- TEAEs leading to permanent withdrawal of study medication.
- TEAEs with a fatal outcome.
- All TEAEs by maximum relationship.
- Serious TEAEs by maximum relationship.
- TEAEs with a fatal outcome by maximum relationship.
- All TEAEs by maximum intensity.
- Non-serious TEAEs reported by more than the reporting threshold of 5% of subjects. The cut-off will be applied before rounding on each treatment group and overall.

A further summary will be presented by treatment group at completion of AS0008 and overall displaying the frequency of TEAEs by descending frequency of PT.

An additional table will be presented by MedDRA SOC, HLT and PT, by treatment at time of AE onset (BKZ 160mg, BKZ 320mg and BKZ Total) for all TEAEs in AS0009 and all TEAEs that were ongoing from AS0008 at the time of the AS0009 EV. Ongoing TEAEs are defined as TEAEs that started prior to the AS0009 EV and continued after the first dose of study medication in AS0009.

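### The AS0009 table that measures withdrawal due to TEAEs selects by AE onset date, so it omits AS0009 withdrawals caused by unworsened bimekizumab TEAEs carried over from AS0008

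*SAP*

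**What the plan says.** SAP 2.2.1.2 defines the secondary safety variable as withdrawal from the study due to TEAEs and gives its measure: "This is measured by the incidence of TEAEs leading to study discontinuation and/or permanent withdrawal of study medication". SAP 10.2 plans a table by SOC, HLT and PT for "TEAEs leading to study discontinuation and/or permanent withdrawal of study medication", by treatment group at completion of AS0008 and overall. No exception to the onset rule and no combined AS0008 and AS0009 version is stated for that table.

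The default selection rule, also in SAP 10.2, is "AE summaries will, in general, include only events with onset on or after the start date of study treatment in AS0009". The same section defines treatment-emergence by onset: "TEAEs are those with onset date on or after the start date of study medication in AS0009".

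For events still ongoing when AS0008 ended, SAP 10.2 sets three further rules:

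- Status: "Events that were ongoing at the end of AS0008 will have their treatment-emergent status taken from the AS0008 database".
- Onset: "Onset date (and derived variables) will be taken from the AS0008 database".
- Consequences: "End date, outcome, actions taken and seriousness will be taken from the AS0009 database".

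The TEAE overview has separate rows for "TEAE leading to study discontinuation, TEAE leading to permanent withdrawal of study medication". It is repeated on AS0008 and AS0009 data combined for the AS0009 Safety Set, without events that began on placebo.

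**The concern.** The variable describes something that happens in AS0009: a subject stops the study or the drug because of a TEAE. The table that measures it is filtered on when the AE began, not on when it led to withdrawal. Every AS0009 subject enters after 36 or 48 weeks on bimekizumab (SAP 2.2.1.3), and ongoing AEs are expected at entry, because protocol 9.1.1 requires them to be captured and followed. A bimekizumab TEAE that starts late in AS0008 and leads to withdrawal early in AS0009 is therefore foreseeable.

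Such a withdrawal cannot be an AS0008 withdrawal either, since the subject completed that study. At stake is a named secondary safety variable in a study whose primary objective is safety. The onset rule can remove withdrawals from this table but cannot add any.

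**Working it through.** The plan states no figure for this variable and has no formal sample size (SAP 2.4), so there is nothing to reproduce. The check applies the SAP's counting rules to four kinds of subject, each withdrawing in AS0009 because of an AE that is treatment-emergent.

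Inputs:

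- the onset rule and the carry-over rules in SAP 10.2;
- the worsening rule in protocol 9.1.7, under which an AE that increases in intensity is reported again with a new start date;
- the exclusion of placebo-onset events from the combined overview in SAP 10.2.

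| Event leading to AS0009 withdrawal | AS0009 withdrawal table | Combined AS0008 and AS0009 overview |
|---|---|---|
| Onset in AS0009 | counted | counted |
| Carried over, bimekizumab onset, intensity unchanged | not counted | counted |
| Carried over, worsened in AS0009 (new record) | counted | counted |
| Carried over, placebo onset | not counted | not counted |

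The second line is the gap. The record is a TEAE by the status rule and shows withdrawal by the consequences rule, but the onset rule excludes it. The AS0009-only overview rows for withdrawal omit it in the same way.

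Next, where that subject does appear as a withdrawal:

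- **Combined overview (SAP 10.2).** The subject is counted here. However, the output has no SOC, HLT or PT detail and does not separate carried-over events. It shows study discontinuation and drug withdrawal as two rows, not the and/or measure of SAP 2.2.1.2. Its columns are BKZ 160mg, 320mg and Total (SAP 3.7), not treatment group at completion of AS0008.
- **Disposition (SAP 5.1).** Discontinuations due to AEs are summarised for the Safety Set with no onset rule stated, so the subject falls within this summary.
- **Listing (SAP 10.2).** AEs leading to study discontinuation are listed, so the event is there if the AE led to study discontinuation.
- **Table of AS0009 TEAEs plus those ongoing from AS0008 (SAP 10.2).** It covers all TEAEs and does not pick out those leading to withdrawal.

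Size. The documents do not give k, the number of subjects affected. With k assumed and N = 285, the maximum enrolment in SAP 2.4, the shortfall in the reported percentage is 100 × k / N:

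- k = 1: 100 × 1/285 = 0.35 points
- k = 3: 100 × 3/285 = 1.05 points
- k = 5: 100 × 5/285 = 1.75 points
- k = 10: 100 × 10/285 = 3.51 points

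A smaller Safety Set would make each subject worth slightly more.

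**The case against.** The strongest defence is that the onset rule is a stated convention, applied alike to all TEAEs, serious TEAEs and withdrawals. Selecting only the withdrawal tables by action would let a subject count under withdrawal but not under any TEAE in the same overview. That is a fair objection to mixing the two kinds of event in one count. It does not apply to a separate, labelled row that leaves the AS0009-onset count unchanged.

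Differences between disposition, the AS0009 table and the combined overview are also not errors in themselves. The outputs have different scopes, and nothing in the SAP requires them to agree. This stands, and the point does not rest on reconciliation.

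The number affected is likely to be held down. Subjects must have completed AS0008 without meeting withdrawal criteria and be expected to benefit (protocol 6.1). A medically significant active infection is an exclusion, and an ongoing SAE requires consultation with the Medical Monitor before entry (protocol 6.2). Worsened events enter the table as new records. All of this stands and bears on size, but it does not close the gap for an unworsened event.

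A reader might infer more than the documents support, in three ways:

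- That these withdrawals are counted nowhere. They are not lost: the combined overview, disposition and, where it applies, the listing hold them.
- That fatal TEAEs need the same change. The overview already has a fatal AE row beside the fatal TEAE row, based on all subjects enrolled in AS0009, and all deaths are listed.
- That a share of missed withdrawals can be estimated. This would need the lag from onset to withdrawal and the total number of AE withdrawals. The documents give neither, and any simple model would ignore the screening at entry.

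**Conclusion.** The point holds for one table and its companion overview rows. Under the SAP's own rules, the AS0009 output that measures the secondary safety variable omits a withdrawal caused by an unworsened bimekizumab TEAE carried over from AS0008, although the SAP treats that event as treatment-emergent and holds its AS0009 action.

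The effect is descriptive and probably small, at about 0.35 percentage points per subject if N = 285, with the number of subjects unknown. Its direction is fixed: the table can only be too low. The conclusion assumes that the default onset rule applies to this table. The SAP states the rule as a general one and names no exception here. Because it also keeps carried-over events treatment-emergent, two programmers could read it differently, which is a further reason to settle the matter in the text.

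**What to change.** In SAP 10.2, state that the AS0009 tables of TEAEs leading to study discontinuation and/or permanent withdrawal of study medication, and the matching rows of the AS0009 overview, will show:

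1. the count of TEAEs with onset in AS0009, as now planned;
2. a separate row for bimekizumab TEAEs ongoing from AS0008 whose AS0009 record shows study discontinuation or permanent withdrawal of study medication;
3. a total in which each subject is counted once.

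A footnote can say that subjects in the second row need not appear under any TEAE in the AS0009-only overview. The tables of fatal TEAEs need no change.

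The cost is one sentence and one selection flag on data already in the AS0009 database, plus one extra row. The total will be slightly less favourable wherever such withdrawals occurred. No study procedure or clinical rule is affected.

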4.2.2 Handling of missing data for adverse events

A complete date must be established to correctly identify the AE as treatment-emergent. For purposes of imputing missing components of partially reported start and stop dates for AEs, the algorithms listed below will be followed. Start and stop dates of AEs will be displayed as reported in the subject data listings (ie, no imputed values will be displayed in data listings).

Partial or missing start dates for events recorded during AS0008 (including those which were ongoing at the start of AS0009) will be imputed using the imputed start date from the AS0008 database.

Imputation of partial AE start dates for events reported in AS0009 only will follow the rules below (treatment switching rules refer to AS0008 only and data were used directly from the AS0008 database):

- If only the month and year of the AE start date are specified, and the month and year of the start date of study medication in AS0009 are not the same as the month and year of the AE start date, and the subject did not switch treatment during that month and year, then use the 1st of the month of the AE start date.
- If only the month and year of the AE start date are specified, and the month and year of the start date of study medication in AS0009 are not the same as the month and year of the AE start date, and the subject switched treatment during the month and year of the AE start date, then use the date of treatment switch.

- If only the month and year of the AE start date are specified, and the month and year of the start date of study medication in AS0009 are the same as the month and year of the AE start date, then use the start date of study medication in AS0009 (regardless of treatment switching). If this results in a start date after a known end date use the 1st of the month of the AE start date.
- If only the year of the AE start date is specified, and the year of the start date of study medication in AS0009 is not the same as the year of the AE start date, and the subject did not switch treatment during the year of the AE start date, then use the 1st of January of the year of the AE start date.
- If only the year of the AE start date is specified, and the year of the start date of study medication in AS0009 is not the same as the year of the AE start date, and the subject switched treatment during the year of the AE start date, then use the date of treatment switch.

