- If only the year of the AE start date is specified, and the year of the start date of study medication in AS0009 is the same as the year of the AE start date, then use the start date of study medication in AS0009 (regardless of treatment switching). If this results in a start date after a known end date use the 1st of January of the year of the AE start date.
- If only the year and day of the AE start date are specified, and the year of the start date of study medication in AS0009 is not the same as the year of the AE start date, then use January of the year of the AE start date together with the known day.
- If only the year and day of the AE start date are specified, and the year of the start date of study medication in AS0009 is the same as the year of the AE start date, then use the start month of study medication in AS0009 together with the known day.
 - If this results in a start date after a known end date use January of the year of the AE start date together with the known day.
 - If this results in a start date prior to the start date of study medication in AS0009 (in the imputed month) the event will be considered to be treatment-emergent.
- If the AE start date is completely unknown and the AE stop date is unknown or not prior to the start date of study medication in AS0009, then use the start date of study medication in AS0009.

Imputation of partial AE stop date:

- If only the month and year are specified, then use the last day of the month.
- If only the day and year are specified, then use December of that year
- If only the year is specified, then use December 31st of that year.
- If the stop date is completely unknown, do not impute the stop date.

In the event of ambiguity or incomplete data which makes it impossible to determine whether the AE was treatment-emergent, the AE will be considered treatment-emergent. For subjects who may have died during the study, imputed dates will be truncated at the date of death.

If the intensity of an AE is unknown, it is considered as severe. If the relationship to study drug is missing, it is considered as related.

If the seriousness of an AE is unknown, no imputation will be performed. Such events will therefore be excluded from any listings or summaries of SAEs. If the seriousness of an AE is unknown, every attempt should be made to resolve this prior to database lock.

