Exposure Category	Start date	End date	Duration of Exposure
Total exposure to BKZ 160mg	First dose of BKZ 160mg in AS0008 or AS0009	Last dose of BKZ 160mg in AS0009	Minimum of [(End date – start date + 140 ^a) +1] and (Date of last clinical contact ^b – start date + 1)
Exposure to BKZ 320mg	First dose of BKZ 320mg in AS0008	First dose of BKZ 160mg in AS0009 for subjects who were dosed in AS0009 ^c . Last dose of BKZ 320mg in AS0008 for subjects who were not dosed in AS0009	(End date – start date + 1) for subjects who were dosed in AS0009. Minimum of [(End date – start date + 140 ^a) +1] and (Date of last clinical contact ^b – start date + 1) for subjects who were not dosed in AS0009
Exposure to BKZ 160mg in AS0009	First dose of BKZ 160mg in AS0009	Last dose of BKZ 160mg in AS0009	Minimum of [(End date – start date + 140 ^a) +1] and (Date of last clinical contact ^b – start date + 1)
Subjects who died ^d	Start date for each option as above	Date of death	End date – start date + 1

BKZ=bimekizumab.

^a 140 days refer to 5 half-lives of BKZ.^b Date of last clinical contact for each subject is defined as the maximum of [last visit date including SFU visit (including unscheduled SFU visits), last AE start date (including imputed AE start dates), date of study termination or completion, last date of study drug administration following rules for partial treatment end dates as per Section 4.2.4].^c In the event that the first dose in AS0009 was more than 140 days after the last dose in AS0008, the exposure time at risk for 320mg will be calculated using AS0008 end date – AS0008 start date + 140 days.^d For subjects who died, the date of death will be used to replace the end date in the calculation of exposure time at risk only if the subject died within the ‘at risk’ interval (i.e., within 140 days following the last dose [not applicable for duration on BKZ 320mg] or if the subject died before dosing in AS0009 (for time at risk on BKZ 320mg). If the subject died more than 140 days after the last dose of BKZ in AS0009 the exposure time at risk will be calculated using the ‘at risk’ interval of 140 days. Note that date of death should be equivalent to date of last clinical contact.

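### In former 320 mg subjects, AS0009-only AEs with an unknown start date, or a year-only date in the AS0009 start year, are imputed to the first AS0009 dose and then counted under 320 mg in tables by treatment at onset

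*SAP*

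**What the plan says.** SAP 4.2.2 gives the start-date rules. Their scope is set by "Imputation of partial AE start dates for events reported in AS0009 only will follow the rules below (treatment switching rules refer to AS0008 only"; AEs recorded in AS0008 keep the date from that database. Three branches lead to the first AS0009 dose date:

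- **Wholly unknown date.** The condition, which refers to the first AS0009 dose, is "If the AE start date is completely unknown and the AE stop date is unknown or not prior to the start date of study medication".
- **Year only.** The condition is "and the year of the start date of study medication in AS0009 is the same as the year of the AE start date", and the action is "then use the start date of study medication in AS0009 (regardless of treatment switching").
- **Month and year.** The same action applies when both match the month and year of the first AS0009 dose.

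Other partial dates go elsewhere. For a different month, for example, the instruction is "then use the 1st of the month of the AE start date", if there was no AS0008 treatment switch in that month.

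SAP 10.2 allocates events to a dose in the combined AS0008 and AS0009 summaries: "AEs which occur on the day of a treatment switch will be considered to have begun on the previous treatment". The exceptions are acute anaphylaxis, hypersensitivity reactions, administration-site reactions and injection-site reactions.

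SAP 10.1, Table 10-2, ends 320 mg time at risk on "First dose of BKZ 160mg in AS0009 for subjects who were dosed in AS0009", counted inclusively. Table 10-1 ends 320 mg treatment duration on the same day.

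**The concern.** A switch-day rule makes sense for an onset that was actually reported on that day, when the event may have started before the new dose was given. An imputed date carries no such information. Section 4.2.2 uses the first-dose date as a conservative default that keeps the event treatment-emergent in AS0009. Section 10.2 then reads the same date as evidence about dose.

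Together the two rules move some events first recorded during open-label 160 mg treatment into the 320 mg column. Subjects already on 160 mg at the end of AS0008 are unaffected, because the dose does not change for them at entry, so the shift runs one way. It also runs into the column with far fewer patient-years, where one rare or serious event is easily seen.

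**Working it through.** **Step 1: which records reach the first-dose date.** The documents give no figure to reproduce. I applied the Section 4.2.2 branches to simulated AS0009-only events, 200,000 per branch. Assumptions: entry dates uniform over one calendar year, true onset uniform from the first dose over 204 weeks plus 140 days (or over the first 48 weeks), no AS0008 switch in the reported period, no conflicting stop date.

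| Reported date | Set to first-dose date, full follow-up | Same, first 48 weeks | Of those set, truly that day |
|---|---|---|---|
| Wholly unknown | 100% | 100% | 0.1% to 0.3% |
| Year only | 11.6% | 54.1% | 0.5% to 0.6% |
| Month and year | 1.0% | 4.7% | 6.5% to 6.6% |

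A date with day and year but no month takes the start month with the known day. It equals the first-dose date only by coincidence (0.4% and 2.0%) and is not part of this point.

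**Step 2: an illustration.** Take a former 320 mg subject first dosed in AS0009 on 11 December 2017, and an AE outside the four exception categories.

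- Wholly unknown start, true onset June 2020: imputed to 11 December 2017, counted under 320 mg.
- Reported as 2017: imputed to 11 December 2017, counted under 320 mg.
- Reported as December 2017: imputed to 11 December 2017, counted under 320 mg. True onset is within weeks of that day and may precede the dose.
- Reported as June 2018: imputed to 1 June 2018, stays on 160 mg.
- Reported as 2018: imputed to 1 January 2018, stays on 160 mg.

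**Step 3: where it shows.** SAP 10.2 plans TEAE and serious TEAE tables for the two studies combined by treatment at onset, with EAIR and EAER. It also plans an n-and-percentage table of AS0009 TEAEs plus those ongoing from AS0008, again by treatment at onset. These tables are affected. The AS0009-only tables use the treatment group at the end of AS0008 (SAP 3.7), so they do not change. BKZ Total counts the event once either way.

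**Step 4: weight of one moved event.** EAER = 100 × events / patient-years, so one event adds 100 / patient-years. SAP 2.2.1.3 puts bimekizumab treatment before entry at 36 or 48 weeks. The number of 320 mg subjects is not given; I assume 100 to 150.

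- 100 subjects, 36 weeks: 100 × (36 × 7 + 1) / 365.25 = 69.3 PY; 100 / 69.3 = 1.44 per 100 PY.
- 150 subjects, 48 weeks: 150 × (48 × 7 + 1) / 365.25 = 138.4 PY; 100 / 138.4 = 0.72 per 100 PY.

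On the 160 mg side, 285 subjects with full AS0009 follow-up give 285 × (204 × 7 + 141) / 365.25 = 1224.3 PY, where one event is worth 100 / 1224.3 = 0.08 per 100 PY. The gain in the 320 mg column is therefore much larger than the loss in the 160 mg column.

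**The case against.** **Is AS0009 entry a treatment switch?** Section 10.2 does not say so, and Section 4.2.2 limits treatment-switching rules to AS0008. This is a fair point, and that step is inferred. However, the limitation sits in the imputation rules. The switch-day rule introduces summaries that span both studies, and Tables 10-1 and 10-2 end 320 mg time on the first AS0009 dose. The inference is the better reading, but the SAP should make it explicit.

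**Are such dates rare?** Probably. Site visits are at most 12 weeks apart, AEs are prompted at each visit (protocol 9.1.4), and SAEs must be reported within 24 hours of the site learning of them (protocol 9.1.13). A serious event with no known year should be uncommon. Listings show dates as reported, so affected records can be found. This limits the size of the problem but does not remove it.

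**Month-year dates.** A reader might infer that every event imputed to that day is misassigned. The documents do not support this. A month-year date reaches that day only in the month of the first dose, and AEs are collected from consent, so onset may truly precede the dose. I leave that branch alone.

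**Conflict between tables.** A reader might also infer that one event carries two doses in one report. It does not: the AS0009-only tables label former 320 mg subjects by their AS0008 group, as SAP 3.7 states.

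**Conclusion.** The point holds for wholly unknown dates and for year-only dates in the AS0009 start year, among AEs reported only in AS0009 by former 320 mg subjects and outside the four exception categories. As written, the SAP counts them under 320 mg in tables by treatment at onset, although onset was very probably on 160 mg. This is a minor defect.

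The size per event is 0.72 to 1.44 per 100 PY on the 320 mg EAER, under the assumed 100 to 150 subjects. The total is unknown because the number of such records is not documented.

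A percentage inflation is tempting but would only restate an assumption. Subject numbers and the AE rate cancel, leaving p × AS0009 years / years on 320 mg, where p is the share of AS0009 AEs with such dates. With p from 0.5% to 2%, 3.0 to 4.3 AS0009 years and 0.78 year on 320 mg, this runs from 0.005 × 3.0 / 0.78 = 1.9% to 0.02 × 4.3 / 0.78 = 11.0%. Nothing in the documents supports that range of p. Nor do all incomplete dates follow this path: Step 1 shows that most month-year dates stay on 160 mg.

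**What to change.** In SAP 10.2, state that the first AS0009 dose is a treatment switch for former 320 mg subjects, and add:

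> AEs reported in AS0009 only whose start date was completely unknown, or year-only, and was imputed to the first AS0009 dose date under Section 4.2.2 are assigned to BKZ 160mg in tables by treatment at AE onset.

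Leave the switch-day rule unchanged for reported dates, for month-year dates and for AEs taken from the AS0008 database. Restricting it to complete reported dates would be too broad: AS0008 events with imputed dates would have no rule, and first-month events that truly began before the dose would be sent to 160 mg.

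The cost is two sentences in the SAP and one programming condition. No new data are needed.
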